- Stability: McMurray test; Apley's Grind test, patellar tilt test, patellar grind test, patellar apprehension test
- Strength: Muscle strength (quadriceps, hamstrings, Iliopsoas)
- Range of Motion: Passive and active ROM.
- Sensation: Reflexes, function, sensation, etc. (normal/abnormal)
- Posture/alignment: leg length discrepancy, foot position, etc.
- Standard Radiographic Testing: AP and Lateral x-ray views of the knee (to determine K-L grade)
These x-rays are part of the standard practice when examining patients who present with osteoarthritis of the knee;
- Complete Patient Reported Outcome Questionnaires:
 - Western Ontario and Mac Master University (WOMAC)
 - Visual Analogue Scale (VAS) pain tool
 - Short-Form 36 (SF-36)
 - Creation of a treatment plan for the patient (time of usage, instructions of use etc...)

The following standard of care procedures will be conducted at the treatment center located at [name]:

- AposTherapy® device calibration according to patient's allocation

VISIT 3 & 4 – Three and Seven Week Follow Up

The following standard of care procedures will be conducted at the treatment center located at [name]:

- AposTherapy® device adjustment

VISIT 5 – 12 Weeks (3 Month) Follow Up (between 76-104 days after baseline)

The following procedures will be conducted at the physician's office located at NYULMC Center for Musculoskeletal Care, [name]):

- Physical Knee Evaluation (same as screening/baseline)
- Adverse/Reportable Event review
- Review concomitant medications
- Complete Patient Reported Outcome Questionnaires:
 - Western Ontario and Mac Master University (WOMAC)
 - Visual Analogue Scale (VAS) pain tool
 - Short-Form 36 (SF-36)
- Compliance Follow-Up

The following standard of care procedures will be conducted at the treatment center located at [name]:

- AposTherapy® device adjustment

VISIT 6 – 18 Weeks Follow Up

The following standard of care procedures will be conducted at the treatment center located at [name]:

- AposTherapy® device adjustment

VISIT 7 – 24 Weeks (6 Month) Follow Up (between 150-210 days after baseline)

The following procedures will be conducted at the physician's office located at NYULMC Center for Musculoskeletal Care, [name]):

CONFIDENTIAL

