This material is the property of the NYU School of Medicine and Langone Medical Center. Do not disclose or use except as authorized in writing by the study sponsor

- Physical Knee Evaluation (same as screening/baseline)
- Adverse/Reportable Event review
- Review concomitant medications
- Un-blinding of patient allocation and beginning of Phase II of the study
- Complete Patient Reported Outcome Questionnaires:
 - Western Ontario and Mac Master University (WOMAC)
 - Visual Analogue Scale (VAS) pain tool
 - Short-Form 36 (SF-36)
 - Subject Satisfaction Questionnaire
- Compliance Follow-Up

The following standard of care procedures will be conducted at the treatment center located at [name]:

- AposTherapy® device adjustment
- Administer device (for patients who have crossed over from control to active)

VISIT 8 – 27 Weeks Follow Up (only for patients that crossed-over from the control to intervention group)

The following standard of care procedures will be conducted at the treatment center located at [name]:

- AposTherapy® device adjustment

VISIT 9 – 36 Weeks Follow Up

The following procedures will be conducted at the physician's office located at NYULMC Center for Musculoskeletal Care, [name]): (Cross-Over Patient's Only)

- Physical Knee Evaluation (same as screening/baseline)
- Adverse/Reportable Event review
- Review concomitant medications
- Complete Patient Reported Outcome Questionnaires:
 - Western Ontario and Mac Master University (WOMAC)
 - Visual Analogue Scale (VAS) pain tool
 - Short-Form 36 (SF-36)
- Compliance Follow-Up

The following standard of care procedures will be conducted at the treatment center located at [name]:

- AposTherapy® device adjustment

VISIT 10 – 42 Weeks Follow Up

The following standard of care procedures will be conducted at the treatment center located at [name]:

- AposTherapy® device adjustment

VISIT 11 – 52 Weeks (1 year) Follow Up

The following procedures will be conducted at the physician's office located at NYULMC Center for Musculoskeletal Care, [name]):

- Physical Knee Evaluation (same as screening/baseline)
- Adverse/Reportable Event review
- Review concomitant medications
- Complete Patient Reported Outcome Questionnaires:

CONFIDENTIAL

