Patients that were allocated to the control group will receive the AposTherapy® device and treatment. The device, with calibrated elements, will be individually calibrated to the patients according to his/her clinical condition. During their daily routine, patients will be asked to wear their custom-worn device for approximately 2 hours per day, throughout the study duration, starting with less than an hour of walking around the house and gradually increasing wearing time to outdoor walking. Patients that crossed from the control group to the active group will be assessed after 3 months and 6 months from commencement of phase II. The results of the 6 months will serve as their new baseline results for phase II of the study. Patients will be asked to come to follow-up visits at the treatment center (located at [name]) at the following time points: 27 weeks from original baseline, 36 weeks from original baseline, 42 weeks from original baseline, and 52 weeks from original baseline. During these visits the biomechanical device will be adapted according to the clinical needs of the patient.

CONFIDENTIAL

This material is the property of the NYU School of Medicine and Langone Medical Center. Do not disclose or use except as authorized in writing by the study sponsor

Study schedule:

Study Periods	Screening	Treatment, Intervention Period									
		1	2	3	4	5	6	7	8	9	10
Time (week)	-2	0	3	7	12	18	24 – final assessment for phase I, un-blinding patients, cross-over design and commence of phase II	27 – only for patients that crossed-over from the control group to the intervention group	36	42	52
Patient Information and Informed Consent (at NYULMC)	X										
Demographics (at NYULMC)	X										
Medical History (at NYULMC)	X										
In- /Exclusion Criteria (at NYULMC)	X										
Full Research Assessment (Physician) (at NYULMC)	X				X		X		X		X
Radiography (at NYULMC)	X										
Randomization (at NYULMC)	X										
Concomitant Therapy (at NYULMC)	X				X		X		X		X
Primary Variables (at NYULMC)	X				X		X		X		X
Secondary Variables (at NYULMC)	X				X		X		X		X
Adverse Events (at NYULMC)					X		X		X		X
Administer Medical Device (at Apos Center)		X					X – for patients who crossed-over from control to active				
Adjustment Medical Device (at Apos Center)			X	X	X	X	X – active group	X	X	X	X

CONFIDENTIAL

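### The cross-over group's Phase II outcome assessments have two unreconciled time anchors, which matters mainly for the 3-month result

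*Combined protocol and SAP*

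**What the plan says.** The Phase II section under Methods and Procedures says that patients who move from the sham to the active device "will be assessed after 3 months and 6 months from commencement of phase II", with their Phase I 6-month scores as the Phase II baseline. Later in the same paragraph it lists the treatment-center visits, at which the device is adapted: "27 weeks from original baseline, 36 weeks from original baseline, 42 weeks from original baseline, and 52 weeks from original baseline".

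The visit list puts the outcome questionnaires on the calendar scale. WOMAC, VAS and SF-36 are collected from cross-over patients at "VISIT 9 – 36 Weeks Follow Up" and again at "VISIT 11 – 52 Weeks (1 year) Follow Up". Neither entry has a window. The Study schedule table marks the primary and secondary variables in the same week-36 and week-52 columns.

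The entry for Visit 7 includes "Un-blinding of patient allocation and beginning of Phase II of the study" and the issue of the active device to patients coming from control. Visit 7 is labelled week 24 but may take place "between 150-210 days after baseline". The 3-month visit of Phase I has a window of days 76 to 104.

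In the endpoint lists, WOMAC after 6 months of the active device in cross-over patients is a Phase II primary endpoint. Their 3-month WOMAC is secondary, as are VAS and SF-36. The Data Analysis section compares cross-over scores at baseline, 3 months and 6 months and states no use of actual time on the device.

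**The concern.** The same outcome visits are timed by two rules that agree only when Visit 7 falls near week 24. A coordinator booking from the visit list or the table would use calendar weeks. One booking from the Phase II text would count from the cross-over date. The protocol does not settle which is meant.

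This matters because the cross-over result is a before-after change with no concurrent sham group, so time on the active device is part of what is being estimated. Under the calendar rule, each day that Visit 7 is late takes a day off the exposure at both later assessments. Late attenders would then have systematically shorter exposure under the same 3-month or 6-month label.

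**Working it through.** **Inputs**

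- Cross-over day *c*: 150 to 210 (Visit 7 window, 61 possible days); on schedule, week 24 × 7 = day 168.
- Calendar assessments: week 36 × 7 = day 252; week 52 × 7 = day 364.
- The protocol's own tolerances in Phase I: 76 to 104 days for 3 months, 150 to 210 days for 6 months.
- Assumptions: the active device is issued on the Visit 7 date, and weeks 36 and 52 are kept exactly, since no windows are given.

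**Formula.** Days on device = 7 × visit week − *c*.

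**On-schedule case first.** With *c* = 168, week 36 gives 252 − 168 = 84 days (12 weeks) and week 52 gives 364 − 168 = 196 days (28 weeks). Both lie inside the Phase I windows, so the two anchors are compatible when Visit 7 is on time.

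**Across the permitted window**

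| Assessment | *c* = 150 | *c* = 168 | *c* = 210 | Phase I window |
|---|---|---|---|---|
| Week 36, nominal 3 months | 252 − 150 = 102 | 84 | 252 − 210 = 42 | 76–104 |
| Week 52, nominal 6 months | 364 − 150 = 214 | 196 | 364 − 210 = 154 | 150–210 |

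- Week 36: the range is 6.0 to 14.6 weeks, a ratio of 102 / 42 = 2.4. Exposure is under 76 days when *c* exceeds 252 − 76 = 176, that is, for cross-over on days 177 to 210. These are 34 of the 61 permitted days. That counts days in the window and does not estimate the share of patients.
- Week 52: the range is 22.0 to 30.6 weeks, a ratio of 214 / 154 = 1.4. Exposure exceeds 210 days only when *c* is below 364 − 210 = 154 (days 150 to 153), and it never falls below 150.

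**Effect of a single anchor.** If the assessments were counted from the cross-over date with the Phase I windows, the 3-month spread would fall from 102 − 42 = 60 days to 104 − 76 = 28 days. The 6-month spread would stay at 210 − 150 = 60 days.

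**The case against.** The best reply is that the Phase II text already states the rule for assessments. On that reading the week labels are nominal, as week 24 plainly is with its 60-day window, and no mixing of exposures follows. The reply also notes that on-schedule patients are fine under either rule, that the randomized Phase I comparison is untouched, and that duration of device use is among the data captured under the monitoring plan. All of this is fair. It does not remove the conflict, because the visit list and the table put the questionnaires at weeks 36 and 52 with no windows, and no stated analysis uses the exposure data.

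Three stronger readings are tempting, and the documents do not support them.

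- A reader might take the sentence listing weeks 27, 36, 42 and 52 as fixing the outcome assessments. It concerns treatment-center visits for adapting the device. The calendar timing of outcomes comes from the visit list and the table, and the mixing of exposures follows only if those override the assessment sentence.
- A reader might infer that the 6-month primary endpoint mixes very different exposures. Its range of 154 to 214 days is the Phase I window shifted by four days.
- A reader might infer that the week-27 adjustment (day 189) can precede issue of the device, because 189 − 210 = −21. Visit 8 applies only to patients who have already crossed over, so that is too literal.

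**Conclusion.** The concern holds as an unresolved contradiction in the protocol: two anchors for the cross-over outcome assessments, and no statement of which governs. If the calendar weeks are followed, time on device at the nominal 3-month assessment runs from 42 to 102 days and falls short of the protocol's own 3-month window for any cross-over after day 176. That affects secondary endpoints. At the nominal 6-month assessment, the Phase II primary endpoint, the effect is small.

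The ranges rest on device issue at Visit 7 and on exact attendance at weeks 36 and 52. Without windows for those visits, the actual spread could be wider. How many patients would be affected depends on when Visit 7 takes place in practice, which the documents cannot show.

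**What to change.** Reconcile the Phase II text, the visit list and the schedule table so that the cross-over outcome assessments have one anchor: the date on which Phase II starts and the active device is issued, as the assessment sentence already implies. State windows for Visits 9 and 11 in cross-over patients, for example no wider than those of Phase I. Record actual days since device issue and use them in the cross-over analysis, at least by reporting their distribution and analysing change by time since issue. A gain in precision of timing at 6 months would need a window narrower than 60 days.

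The timing of the device-adjustment visits also has to be reconciled by the sponsor. No clinical schedule is proposed here.

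The cost is mostly wording, plus some extra follow-up. Taking 6 months as 26 weeks (182 days), a patient who crosses over on day 210 is due on day 210 + 182 = 392. That is 28 days, or four weeks, after week 52. If a 6-month window running to day 210 were used in full, the last date would be day 420, eight weeks after week 52. The 12-month duration given in the Study Summary and the recruitment section must allow for this.

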This material is the property of the NYU School of Medicine and Langone Medical Center. Do not disclose or use except as authorized in writing by the study sponsor

Data Analysis

Phase I:

- Primary outcome measures will include comparing scores at baseline and the following study time points (baseline, 3 months and 6 months) obtained from the WOMAC. The WOMAC is a validated outcomes assessment used to measure patients' opinion about their knee and associated problems.
- Secondary outcome measures will include comparisons of all measured variables between baseline and all time points including VAS score, SF-36 score, improvement and maintenance in knee function using physical examination findings (these include, but are not limited to: Pain, Knee Effusion, Ligament Stability, Stability, Strength, Range of Motion, Sensation, Posture/alignment); and monitoring usage of rescue medications or NSAIDs. All data will be obtained from the completed case report forms that are being utilized for this study.

Phase II:

- Original active group – evaluating the changes in pain, function, quality of life and usage of rescue medications or NSAIDs following 12 months of therapy.
- Cross-over group – comparing scores at baseline and the following study time points (baseline, 3 months and 6 months) obtained from the WOMAC, SF-36, knee function and usage of rescue medications or NSAIDs.

DATA SAFETY MONITORING PLAN (DSMP)

I. Study Monitoring

The principal investigator, [name], will be the data safety monitor for this project. After a three (3) months follow-up period, [name] will review the data for SAE's, protocol deviations and other issues. If it is determined that certain events occur above an expected rate (i.e. increased knee pain), then enrollment will be stopped.

II. Types of Data

Under this DSMP, the following data/events will be captured and documented:

- Duration of AposTherapy® use;
- Monitoring of patient falls;
- Patient Outcomes Assessments;
- Reportable and/or adverse events
- Protocol Deviations

III. Responsibilities and roles for gathering, evaluating and monitoring the data:

Principal Investigator

After a three (3) months follow-up period, the PI will meet with any co-investigators and the Research Coordinator to discuss the current findings and analysis. During these meetings, the PI will also be responsible for verifying data accuracy, and compliance with the study protocol.

Research Coordinator

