The Research Coordinator will be responsible for providing data management support to the PI by collecting and documenting the required study data. This information will be documented in a secure Microsoft Excel spreadsheet with appropriate headings to distinguish the various types of data/events. The Research Coordinator will meet with the PI and any co-investigators to discuss the current findings/analysis, concerns/issues (unanticipated problems and adverse events), and the overall study in general.

IV. Reporting Adverse Events and Unanticipated Problems to the Monitoring Entity

All reportable events will be sent to the IRB in accordance with the timeframes specified by NYU SoM guidelines. The Principal Investigator will have the responsibility of completing and submitting a Reportable New Information (RNI) form to the IRB through Research Navigator.

CONFIDENTIAL

This material is the property of the NYU School of Medicine and Langone Medical Center. Do not disclose or use except as authorized in writing by the study sponsor

V. Assessments

After a three (3) months follow-up period, and then at 6 months and 12 months after the study start, the Principal Investigator, Co-Investigator(s) and Research Coordinator will review and assess the data and/or events captured under the DSMP.

VI. Criteria for Action

Should there be an event or series of events that occur that increases the risks to the participants, the “following steps” will be taken:

1. An investigation into the event will be conducted;
2. If required, a Reportable New Information (RNI) form will be submitted to the IRB;
3. All primary study staff (PI, Co-I, Research Coordinator) will be notified;
4. After a review,
 - a. The protocol may be modified;
 - b. The study may be suspended; or
 - c. A decision may be made to close out the study

VII. Procedures for Communicating – dissemination of safety information

Outcomes of monitoring reviews will be communicated to the IRB through a yearly summary that will include a narrative on all adverse and reportable events (previously reported or not, serious or not), as well as any proposed changes to the protocol and/or study analysis.

Data Storage and Confidentiality

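### Formal adverse event review is scheduled only at weeks 12, 24, 36 and 52, not at the device-only visits, and falls have no stated collection point

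*Combined protocol and SAP*

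**What the plan says.** - **Adverse events.** In the Study schedule table the row "Adverse Events (at NYULMC)" is marked at weeks 12, 24, 36 and 52. Under Phase I Study Visits, which lists all visits to week 52, adverse event review appears at those visits and no others.
- **Device visits.** The row "Adjustment Medical Device (at Apos Center)" is marked at weeks 3, 7, 12, 18, 24 (active group), 27, 36, 42 and 52. The entry "VISIT 3 & 4 – Three and Seven Week Follow Up" contains device adjustment only, as do the entries for weeks 18, 27 and 42. Week 27 is for cross-over patients only.
- **Windows.** The first two reviews are headed "VISIT 5 – 12 Weeks (3 Month) Follow Up (between 76-104 days after baseline)" and "VISIT 7 – 24 Weeks (6 Month) Follow Up (between 150-210 days after baseline)". Weeks 36 and 52 have no window.
- **Week 36.** The visit list marks the office procedures "Cross-Over Patient's Only". The table does not.
- **Falls.** DSMP section II lists "Monitoring of patient falls" among the data to be captured. No visit list or table row mentions falls.
- **General question.** The text after Outcome Measure Evaluation Criteria has subjects asked, at every follow-up visit, about changes in knee symptoms or overall health, with research personnel recording when they occurred.
- **Safety reviews.** DSMP section V places them after three months of follow-up "and then at 6 months and 12 months after the study start".

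**The concern.** Patients begin walking on convex pods at week 0 and build up wearing time from under an hour indoors to outdoor walking. Cross-over patients do the same from week 24. Falls and pain flares seem most likely to arise then, and the plan itself treats falls as relevant: it excludes patients prone to falling and discusses fall reports under device risk. Yet the first formal question comes about three months later, although patients attend for adjustment at weeks 3 and 7.

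Short-lived early events may be forgotten or misdated over that interval. This weakens the comparison of harms between arms. It also weakens the check in DSMP section I, under which enrollment stops if events such as increased knee pain exceed an expected rate, because that check needs complete, dated events.

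**Working it through.** The plan states no figure on this point, so the check compares the schedule table with the visit lists and measures the intervals between reviews. Weeks are converted at 7 days and months at 30.44 days. Baseline is taken as week 0, the day of fitting.

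**Step 1. Device visits without a review.** Removing the review weeks {12, 24, 36, 52} from the device weeks {3, 7, 12, 18, 24, 27, 36, 42, 52} leaves weeks 3, 7, 18, 27 and 42. Table and visit lists agree on this.

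**Step 2. Intervals between formal reviews.**

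| Interval | Nominal | At window limits |
|---|---|---|
| Fitting to week 12 | 12 × 7 = 84 days (2.8 months) | 76 to 104 days (2.5 to 3.4 months) |
| Week 12 to 24 | 84 days | up to 210 − 76 = 134 days (4.4 months) |
| Week 24 to 36, cross-over | 84 days | 252 − 210 = 42 to 252 − 150 = 102 days |
| Week 36 to 52, cross-over | 16 × 7 = 112 days (3.7 months) | no window given |
| Week 24 to 52, original active arm, visit-list reading | 28 × 7 = 196 days (6.4 months) | 364 − 210 = 154 to 364 − 150 = 214 days |

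The limits in the third and fifth rows assume week 36 on day 252 and week 52 on day 364. The table puts screening at week −2. If baseline were dated from then, the first review would fall 76 − 14 = 62 to 104 − 14 = 90 days after fitting.

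**Step 3. Phase II visits of the original active arm.** Four places differ:
- Active Arm Process lists treatment-center visits at weeks 27, 36, 42 and 52.
- The Phase II section names only week 52 for this arm, at both the office and the treatment center.
- The visit list restricts the week 36 office procedures and the week 27 visit to cross-over patients, but not week 42.
- The table restricts week 27 only.

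The 28-week gap follows from the visit list and the Phase II section. On the table, week 36 would split it into 12 and 16 weeks.

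**Step 4. Does the general question fill the gap?** The arm descriptions call treatment-center visits follow-up visits, which favors the wider reading. Against that, the rescue-medication and compliance questions are tied to the same visits in the same text, yet medication review and compliance follow-up are itemized only at office visits. The narrower reading is more likely, but the text does not settle it. Falls are not named on either reading.

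**Step 5. Effect of asking at existing device visits.** The Phase I start-up gap of 12 weeks becomes 3, 4 and 5 weeks (0–3, 3–7, 7–12). The cross-over gap of 12 weeks becomes 3 and 9 (24–27, 27–36). For the original active arm, a question at week 42 but none at week 36 still leaves 42 − 24 = 18 weeks; if only week 52 is attended, all 28 remain.

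**Step 6. Timing of safety reviews.** If the DSMP clock is calendar time, a patient enrolled *t* months after study start has 12 − *t* months of follow-up at the last listed review, so anyone enrolled after the first day is still on study. If the clock runs per patient, this does not arise. The document does not define it.

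**The case against.** The strongest reply is that the general question already has staff asking about, and dating, pain, swelling and health changes at every follow-up visit, and the week 3 and 7 visits carry that name. This stands as a possible reading. A reader might infer that nobody asks about harms at the device visits; the documents do not support that as a flat statement. They support saying that formal review is not scheduled there.

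Two other inferences go too far:
- **That a problem cannot be acted on before week 12.** DSMP section VI is triggered by events, not visits. Section IV sends reportable events to the IRB within institutional timeframes. Patients may withdraw at any point, and staff see them at weeks 3 and 7.
- **That late-enrolled cross-over patients have no planned safety review.** Each has adverse event reviews at weeks 36 and 52, and DSMP section VII requires a yearly IRB summary of all events. The calendar reading of the DSMP clock is also not certain: the Study Summary gives a 12-month study duration and the recruitment section uses the same 12 months for each patient.

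It is also fair that the device is listed as class I, that patients with knee buckling or a tendency to fall are excluded, and that the primary WOMAC comparison is unaffected. These points limit the seriousness. They do not supply a falls question or an earlier formal review.

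**Conclusion.** The point holds as a gap in scheduled elicitation. Followed as written, the schedule puts the first formal adverse event review 76 to 104 days after baseline. That is probably after most of the wear-time build-up, although the protocol gives no duration for it. Cross-over patients nominally wait 12 weeks after receiving the calibrated device. The original active arm goes 28 weeks without a formal review if the visit list governs. Falls collection is unspecified at every visit, including weeks 12, 24, 36 and 52.

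The day counts assume that baseline is the day of fitting and that weeks 36 and 52 fall on their nominal days. The practical gap is smaller if the general question was meant to cover treatment-center visits. The change is worth making because it improves harms capture at little cost; it does not bear on the validity of the primary analysis.

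**What to change.** 1. Add a scripted adverse event and fall question to the treatment-center procedures at weeks 3, 7, 18, 27 and 42, in both the visit lists and the Study schedule table. Use the same form in both arms and send it to the coordinator.
2. Add the fall question to the existing reviews at weeks 12, 24, 36 and 52.
3. State whether the general symptom and health question applies at treatment-center visits.
4. Reconcile Active Arm Process, the visit list, the Phase II section and the table on which Phase II visits, notably weeks 36 and 42, the original active arm attends. Then place the question so that it reaches that arm; item 1 alone does not ensure this.
5. State whether the DSMP reviews run on calendar or per-patient time. If calendar, continue them until the last patient's week 52 visit.

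**Cost.** One short form at existing device visits, subject to item 4 for the original active arm, and slightly more event reports to process. The main drawback is that staff fitting the pods or the sham can see allocation and would be asking about harms during the blinded phase. Patient self-completion or fixed wording limits this.
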